### 5.1.1.2 Demographics

#### 5.1.1.2.1 Analysis Populations

The distribution of subjects within the analysis populations will be summarized as follows:

**Table 5-5 Analysis Population Summaries**

Endpoint	Description	Timing	Methodology
Screened Population	Distribution overall and within countries/regions/sites in total	Screening Period,	Categorical counts

mITT, PP and Safety populations	Distribution overall and within countries/regions/sites in total and by treatment group	Treatment Period	Categorical counts
---------------------------------	---	------------------	--------------------

### 5.1.1.2.2 Subject Disposition

Subject disposition encompasses the distribution of subjects who enter, complete, and discontinue each specified analysis period, along with eCRF-reported discontinuation reasons from each respective analysis period. Subject disposition will be summarized as follows:

**Table 5-6 Subject Disposition Summaries**

Endpoint	Description	Timing	Methodology
Screening and pretreatment disposition	Distribution in the Screened Population in total	Screening Period, Pretreatment Period	Categorical descriptives
Study disposition	Distribution in the mITT Population in total and by treatment group	Treatment Period	Categorical descriptives

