7.1 Analysis Populations

The modified intent-to-treat (mITT) population is defined as all randomized patients with a baseline and at least 1 post baseline assessment of mesopic, high contrast, UNVA and will be analyzed as randomized. The efficacy variables will be analyzed using the mITT population.

[figure not shown]
The per protocol (PP) population is defined as all randomized patients who have no significant protocol deviations that affect the primary efficacy variable and complete all study visits. The PP population will be determined prior to database lock. The primary efficacy variable will also be analyzed using the PP population on an as-treated basis.

The safety population is defined as all patients who received at least 1 dose of study treatment and will be analyzed as treated. All safety measures will be analyzed using the safety population.

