**Table 5-1 Analysis Populations**

Population	Definition	Study Treatment
Screened	All screened subjects who sign informed consent	—
Modified Intent-to-Treat (mITT)	All randomized subjects with a baseline and at least 1 post baseline assessment of mesopic high contrast UNVA, with baseline vary not more than 3 lines across the 5 dosing period, and will be analyzed as randomized.	Randomized assignment
Per Protocol (PP)	All randomized patients who have no significant protocol deviations that affect the primary efficacy variable and complete all study visits for each dosing period.	Actual received
Safety	All subjects who received $\geq 1$ administration of study treatment	Actual received

[figure not shown]

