## 6.8 Analysis Plan Amendment 1 Summary

Following is a summary of content-oriented changes that were made to each section of the protocol, and a brief rationale for these changes. Minor editorial and document formatting revisions have not been summarized.

Section	Revision	Rationale
Section 5.1.1.1.1	mITT definition is changed to 'All randomized subjects with a baseline and at least 1 post baseline assessment of mesopic high contrast UNVA, with baseline vary not more than 3 lines across the 5 dosing period, and will be analyzed as randomized.'	Correction for the primary efficacy baseline data issue.
Section	Age group	Correction

Section	Revision	Rationale
5.1.1.2.4	
 
• 40-47 years
 
• 48-51 years
 
	
[REDACTED]	[REDACTED]	[REDACTED]
[REDACTED]	[REDACTED]	[REDACTED]
[REDACTED]	[REDACTED]	[REDACTED]
[REDACTED]	[REDACTED]	[REDACTED]
[REDACTED]	[REDACTED]	[REDACTED]
[REDACTED]	[REDACTED]	[REDACTED]
[REDACTED]	[REDACTED]	[REDACTED]
Section 5.2.2	UNVA responder analyses with at least a 2-line improvement in mesopic, high contrast UNVA from baseline at a majority of postdose timepoints (6 or more) in the nondominant eye will be added.	Added additional analysis

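### Treatment-period disposition and important protocol deviations are tabulated on the restricted mITT set, so both summaries omit randomised patients excluded from mITT

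*SAP*

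**What the plan says.** SAP section 5.1.1.2.2 sets out what the disposition summary is for: "Subject disposition encompasses the distribution of subjects who enter, complete, and discontinue each specified analysis period", together with the recorded reasons for discontinuing. Table 5-6 has two rows. The treatment-period row is based on "Distribution in the mITT Population in total and by treatment group". The other row covers only the screening and pretreatment periods, as "Distribution in the Screened Population in total", with no split by treatment. Table 5-7 uses the mITT base again for important protocol deviations.

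SAP Table 5-1 defines mITT by two conditions. The first is "All randomized subjects with a baseline and at least 1 post baseline assessment of mesopic high contrast UNVA". The second is "with baseline vary not more than 3 lines across the 5 dosing period". Protocol section 7.1 has only the first: "all randomized patients with a baseline and at least 1 post baseline assessment of mesopic, high contrast, UNVA". SAP section 6.8 shows that Amendment 1 added the second, with the rationale "Correction for the primary efficacy baseline data issue".

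Table 5-1 also defines Screened, Per Protocol and Safety populations. It defines no population of all randomised patients.

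**The concern.** A disposition table should account for everyone who was randomised. Here its base is an efficacy set whose membership depends partly on what happens after randomisation. Protocol section 7.2.1 takes baseline as the hour-0 reading of each dosing period, so the baselines for periods 2 to 5 are recorded after randomisation and after earlier dosing. A patient removed by the 3-line rule then disappears from the summaries that would show whether that patient completed, why the patient left, and which deviations occurred.

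This matters more than usual in this trial. Protocol section 1.4 anticipates that the higher pilocarpine concentration may lead to more discontinuation, and gives this as a reason for varying pilocarpine between patients. Safety and tolerability make up the second clinical hypothesis in protocol section 2.2. Complete discontinuation counts and reasons by randomised group are therefore needed to read the result.

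There is also a mismatch between populations. The Per Protocol set is drawn from all randomised patients and does not carry the 3-line rule. A patient could complete every visit, qualify for Per Protocol and Safety, and still be missing from both disposition and deviations.

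**Working it through.** **Plan's own figures.** SAP section 5.1.2 has 160 enrolled, 10% dropout and 144 completers: 144 / (1 − 0.10) = 160. Protocol section 4.1 has 40 per group, 12.5% dropout and 35 completers: 35 / (1 − 0.125) = 40 per group, or 140 / 0.875 = 160 in all. Both reproduce. The planned number of dropouts is 160 − 144 = 16 (SAP) or 160 − 140 = 20 (protocol). The two documents differ here.

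**Who is missing from Tables 5-6 and 5-7.**
- Patients with no post-baseline UNVA. Randomisation and the first in-office dose both take place at visit 1 (protocol 5.5, 5.8), and the primary variable uses readings from hour 1 (protocol 7.2.1). This group is likely to be small.
- Patients whose period baselines vary by more than 3 lines. The documents give no count. They also do not say how the rule applies to a patient with fewer than five period baselines.

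**Effect on the tabulated rate.** Let D be the number of dropouts, x the dropouts outside mITT and b the completers outside mITT. Then

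apparent discontinuation = (D − x) / (160 − x − b), against D / 160 on all randomised patients.

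The values of x and b below are assumptions.

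| D | x | b | On mITT | On all randomised | Absent from both tables |
|---|---|---|---|---|---|
| 20 | 0 | 8 | 20/152 = 13.2% | 12.5% | 8 |
| 20 | 0 | 16 | 20/144 = 13.9% | 12.5% | 16 |
| 20 | 10 | 0 | 10/150 = 6.7% | 12.5% | 10 |
| 20 | 10 | 8 | 10/142 = 7.0% | 12.5% | 18 |
| 16 | 0 | 16 | 16/144 = 11.1% | 10.0% | 16 |
| 16 | 8 | 8 | 8/144 = 5.6% | 10.0% | 16 |

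**Direction.** Setting (D − x) / (160 − x − b) equal to D / 160 gives x / D = b / (160 − D). The table understates discontinuation when dropouts are excluded from mITT at a higher rate than completers, and overstates it when the reverse holds.

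**Extremes.** If nobody falls outside mITT, nothing changes. If a patient needs all five baselines to satisfy the 3-line rule, and every dropout leaves before the fifth, then x = D and the table shows 0% discontinued against 10.0% or 12.5%.

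**Within one group.** With 5 dropouts among 40 (12.5%), excluding a single dropout gives 4/39 = 10.3%. Excluding a single completer gives 5/39 = 12.8%.

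**The case against.** The strongest reply is that most of this information can be recovered elsewhere and the tables are only descriptive. Several parts of it stand.

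- Table 5-5 counts mITT, Per Protocol and Safety by treatment group. Dosing follows randomisation at the same visit, so Safety is close to all randomised, and Safety minus mITT shows roughly how many were excluded. A reader might infer that differential exclusion would be invisible, but that goes too far. The difference is approximate (Safety is as treated, mITT as randomised), and it does not separate the two exclusion rules or give completion status.
- Adverse events leading to discontinuation are summarised on the Safety population, with listings of the subjects. This covers adverse-event withdrawals only, not other withdrawals or deviations.
- The SAP promises raw and derived listings in a separate specification. Listings may contain the missing patients, but they do not replace a summary by group.
- A reader might infer that every dropout vanishes. A patient who leaves after one post-baseline UNVA, with baselines within the limit, meets both conditions on their face and is tabulated.
- A reader might also infer that the reported discontinuation rates would look too good. The documents do not establish that direction. The range of a patient's baselines cannot shrink as more are recorded, so completers have the most opportunity to fail the 3-line rule. Excluding completers raises the apparent rate.

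What survives is narrower. No summary in the available text gives completion status, the full set of discontinuation reasons, or important deviations for randomised patients outside mITT.

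**Conclusion.** The point holds as a reporting defect that should be corrected. As written, the SAP yields incomplete discontinuation and deviation counts by treatment, and it leaves out the patients removed by a post-randomisation rule that the protocol does not contain. The distortion can go either way. Its size cannot be fixed from the documents, because neither the number failing the 3-line rule nor the handling of incomplete baseline sets is stated. Under the assumed ranges (none to all of the planned dropouts, and 0 to 16 completers, outside mITT), between 0 and 36 of 160 patients (0% to 22.5%) would be absent from both tables. The upper end needs every one of 20 dropouts and 16 completers to be excluded, so it is a bound and not a forecast.

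The primary model and the sample size are unaffected. Whether the 3-line rule is a sound condition for the efficacy population is a separate question. The point here is that its effect should be visible.

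**What to change.** 1. Add an all-randomised population to SAP Table 5-1. The table has no such set at present, so changing the population named in Tables 5-6 and 5-7 is not enough.
2. Base the treatment-period row of Table 5-6, and Table 5-7, on that population, in total and by the four randomised groups. A split by sequence is not needed: 4 groups × 5 sequences = 20 cells of 8 patients would be too sparse to help.
3. Add rows counting patients excluded from mITT by reason, one for no post-baseline UNVA and one for baseline variation over 3 lines.

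The cost is one population definition and a few table rows. No new data are needed.

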### 5.1.1.2.3 Protocol Deviations

Protocol deviations will be defined in a separate document, including importance classification. Protocol deviations will be summarized as follows:

**Table 5-7 Protocol Deviation Summary**

Endpoint	Description	Timing	Methodology
Important protocol deviations	Distribution in the mITT Population in total and by treatment group	Treatment Period	Categorical descriptives

### 5.1.1.2.4 Demographics

Demographics will be summarized for the Screened Population, and in total and by treatment group for the mITT, PP and Safety populations, as follows:

**Table 5-8 Demographic Summaries**

Endpoint	Description	Timing	Methodology
Age	Age (years) relative to informed consent date	Informed consent	Continuous descriptives
Age group	
 
• 40-47 years
 
• 48-51 years
 
	Informed consent	Categorical descriptives
Sex, race, and ethnicity	
 
• eCRF categories
 
• Race group 
 
○ White
 
○ Non-white
 
 
 
• Ethnicity 
 
○ Hispanic
 
○ Non-hispanic
 
 
 
	Screening Period	Categorical descriptives

### 5.1.1.2.5 Baseline Characteristics

Baseline characteristics will be summarized in total and by treatment group for the mITT, PP and Safety populations as follows:

**Table 5-9 Baseline Characteristics Summaries**

Endpoint	Description	Timing	Methodology
Baseline characteristics	
 
Iris color
 
	Latest assessment in Screening Period or Pretreatment Period	Categorical descriptives
Randomization strata	
 
UNVA at baseline of <math>\leq 20/80</math>
 
UNVA at baseline of <math>> 20/80</math>
 
	Randomization date	Categorical descriptives

### 5.1.1.2.6 Medical History

Medical history, encompassing abnormalities and surgeries reported as occurring before the Screening Visit, will be coded using the Medical Dictionary for Regulatory Activities (MedDRA), version 19.0 or newer. Unique subjects who report medical history events will be summarized by MedDRA system organ class (SOC) and preferred term (PT) in total and by treatment group for the Safety Population as follows:

**Table 5-10 Medical History Summary**

Endpoint	Description	Timing	Methodology
Medical history	Abnormalities and surgeries occurring before the Screening Visit	Screening Period	Categorical descriptives

SOCs will be sorted alphabetically; PTs will be sorted in descending frequency in the highest dose group.

### 5.1.1.2.7 Prior and Concomitant Medications

Medications will be listed for the Safety Population as follows:

Medications will be coded using the World Health Organization (WHO) Drug Dictionary, version 14.0 or newer. Unique subjects who reported medications will be summarized by Anatomical Therapeutic Chemical (ATC) 4 class and PT in total and by treatment group for the Safety Population as follows:

**Table 5-11 Medication Summaries**

Endpoint	Description	Timing	Methodology
Prior medications	Medications taken $\geq 1$ time before the study treatment start date, regardless of medication end date	Screening Period, Pretreatment Period	Categorical descriptives
Concomitant medications	Medications taken $\geq 1$ time on or after the study treatment start date, regardless of medication start date 
 
Medications starting 1 day after
 
	Treatment Period	Categorical descriptives

Endpoint	Description	Timing	Methodology
	treatment end date will be listed but excluded from analysis		

ATC4 classes will be sorted alphabetically; PTs will be sorted in descending frequency in the highest dose group.

### 5.1.1.2.8 National Eye Institute Visual Function Questionnaire

National eye institute (NEI) visual function questionnaire - 25 (VFQ-25) that will be administered at screening to determine patient-reported near and distance vision functioning. NEI VFQ-25 will be summarized for the Safety Population.

[figure not shown]
**Table 5-12 NEI VFG-25 Summary**

Endpoint	Description	Timing	Methodology
NEI VFQ-25	NEI VFQ-25 questionnaires	Screening Period	Categorical descriptives

[figure not shown]
### 5.1.1.3 Efficacy Analyses

Efficacy analyses will be based on the mITT Population. The primary efficacy variable, weighted average change from baseline in UNVA letter, will also be analyzed based on the PP population.

The following efficacy assessments are defined:

[Redacted] :

### 5.1.1.3.1 Study Success Criteria

[figure not shown]
There will be no adjustment of type 1 error rate for the multiple tests.

[figure not shown]
### 5.1.1.3.2 Mesopic, High Contrast UNVA

General description of mesopic, high contrast UNVA endpoints.

**Table 5-15 Mesopic, High Contrast UNVA Analyses**

Endpoint	Description	Timing	Methodology
Average change from baseline in UNVA letters (Primary efficacy variable)	Average change from baseline in UNVA letters  in the nondominant eye over two-day dosing periods between hour 1 and hour 10.	Treatment Period	CFB MMRM  CFB ANCOVA  CFB RS figure CFB figure
[REDACTED]	[REDACTED]	[REDACTED]	[REDACTED]
[REDACTED]	[REDACTED]	[REDACTED]	[REDACTED]
[REDACTED]	[REDACTED]	[REDACTED]	[REDACTED]
[REDACTED]	[REDACTED]	[REDACTED]	[REDACTED]
[REDACTED]	[REDACTED]	[REDACTED]	[REDACTED]

### 5.1.1.4.2 Adverse Events

The following adverse event (AE) terms are defined:

**Table 5-23 AE Terms**

Term	Description
Treatment-emergent	An event that initially occurs or increases in intensity on or after the treatment start date, where: 

• Treatment start date <math>\leq</math> event start date <math>\leq</math> following washout period before the next 2-day dosing period or last dose date + 30 days

On-therapy	An event where: 

• Treatment start date <math>\leq</math> event start date <math>\leq</math> following washout period before the next 2-day dosing period or last dose date + 30 days

[figure not shown]
AEs, encompassing abnormalities and surgeries reported as occurring after the Screening Visit, will be coded using MedDRA version 19.0 or newer. Unique subjects reporting AEs in the

following AE categories will be summarized by treatment group and overall for the Safety Population as follows:

[figure not shown]

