Safety measures will be analyzed using the safety population. Medical Dictionary for Regulatory Activities (MedDRA) nomenclature will be used to code adverse events. Incidence rates of each treatment-emergent adverse event will be summarized by primary system organ class and preferred term. Treatment-emergent adverse events are events that occur or worsen after the treatment. Summary tables will be generated for all treatment-emergent adverse events regardless of causality as well as for those considered to be treatment-related. The adverse events will be classified into ocular and nonocular types and will be summarized separately as described below. Ocular adverse events and other ocular evaluations will be summarized using eye as the experimental unit by dosing group and dosing period. Nonocular adverse events and other nonocular assessments (eg, vital signs) will be summarized using patient as the experimental unit by dosing group and dosing period.

Detailed descriptions of the safety analyses for adverse events and other safety measures will be documented in analysis plan.

Sample Size Calculation:

The study consists of 4 parallel groups and 5 sequences of 2-day dosing periods within each group (see Figure 1). Each dosing period is separated by a washout of 14 ± 7 days and each sequence is tested 8 times resulting in 40 patients per group.

The sample size is deemed appropriate to build a response surface model that assesses the efficacy profile of the combination relative to monotherapies.

1. Background and Clinical Rationale

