2.2 Clinical Hypotheses

[figure not shown]
At least one concurrently dosed combination of AGN-199201 and AGN-190584 will:

- demonstrate a significant improvement in UNVA over monotherapy with AGN-199201 and monotherapy with AGN-190584 when they are dosed at the same concentrations as the combination
- 2. produce safety and tolerability findings no worse than cumulative findings with AGN-199201 monotherapy and AGN-190584 monotherapy when they are dosed at the same concentrations as the combination

3. Study Design

This study is a phase 2, multicenter, double-masked, parallel-group, randomized sequence, dose response, vehicle-controlled study in patients with presbyopia. Four groups (see Table 1) of different concentrations of AGN-190584 will be used to compare unfixed combinations with AGN-199201 and a fixed combination of AGN-190584 and a fixed combination of AGN-190584 and AGN-199201 solutions dosed in the nondominant eye during 5 dosing periods. For all 4 treatment groups, each dosing period will be once daily for 2 consecutive days, followed by a 7 to 21 day washout before the next 2-day dosing period, until exit after the fifth 2-day dosing period. The study duration will be 39 to 112 days per patient.

Following a screening visit (days -18 to -1) patients will be randomized at a baseline visit (visit 1) in a 1:1:1:1 ratio (stratified by the UNVA at baseline of $\leq 20/80$ and > 20/80) to 1 of the following treatment groups (also summarized in Table 1):

All patients will receive the fixed combination of AGN-199201 and AGN-190584 ophthalmic solutions within one of the 5 dosing periods. Vehicles for AGN-190584, AGN-199201, and the fixed combination ophthalmic solutions all have the same formulation.

Study medication will be administered once daily in each eye during office visits at hour 0 (8 AM \pm 1 hour) for 2 consecutive days during each dosing period. Dosing periods will be separated by a washout period of 14 ± 7 days. Eyes receiving both AGN-199201 and AGN-190584 are to receive a single drop of AGN-199201, followed approximately 5 to 7 minutes later by a single drop of AGN-190584. Eyes receiving the fixed combination of AGN-190584 and AGN-199201 are to receive a single drop of the fixed combination drug, followed approximately 5 to 7 minutes later by a single drop of vehicle. Eyes receiving vehicle alone are to receive 2 drops of vehicle, separated by approximately 5 to 7 minutes. The study design is depicted in Figure 1.

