9.1 Definitions

9.1.1 Adverse Event

An adverse event is any untoward medical occurrence in a patient or clinical investigation patient administered a pharmaceutical product and that does not necessarily have a causal relationship with this treatment. An adverse event can therefore be any unfavorable and unintended sign (including an abnormal laboratory finding), symptom, or disease temporally associated with the use of a medicinal (investigational) product, whether or not related to the medicinal (investigational) product. In addition, during the screening period, adverse events will be assessed regardless of the administration of a pharmaceutical product.

Note: Adverse events must be collected once informed consent has been obtained, regardless of whether or not the patient has been administered study drug.

Progression of treatment indication including new or worsening of anticipated clinical signs or symptoms, which are collected as clinical efficacy variables and assessed as unequivocally associated with the disease progression and /or lack of efficacy, should NOT be reported as adverse events unless the disease progression is greater than anticipated in the natural course of the disease.

Adverse events will be assessed, documented, and recorded in the electronic case report form (eCRF) throughout the study (ie, after informed consent has been obtained). At each visit, the investigator will begin by querying for adverse events by asking each patient a general,

non-directed question such as "How have you been feeling since the last visit?" Directed questioning and examination will then be done as appropriate. All reported adverse events will be documented on the appropriate case report form.

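### As written, the date condition in SAP Table 5-23 disables the worsening half of the treatment-emergent definition, so events that start before a dose and worsen after it are missed or credited to an earlier treatment

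*SAP*

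**What the plan says.** The Protocol Summary, under Safety, gives the parent definition: "Treatment-emergent adverse events are events that occur or worsen after the treatment". It places no restriction on when the event began.

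SAP Table 5-23 (section 5.1.1.4.2) opens its treatment-emergent row in the same spirit: "An event that initially occurs or increases in intensity on or after the treatment start date, where". The condition that follows has a lower limit, "Treatment start date \leq event start date", and an upper limit for the same start date, "following washout period before the next 2-day dosing period or last dose date + 30 days". The on-therapy row carries an identical condition.

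Protocol 9.1.1 requires collection of events from consent: "Adverse events must be collected once informed consent has been obtained, regardless of whether or not the patient has been administered study drug". Protocol section 3 sets out the timing: "Following a screening visit (days -18 to -1) patients will be randomized at a baseline visit", and each two-day dosing period is "followed by a 7 to 21 day washout before the next 2-day dosing period, until exit after the fifth 2-day dosing period". The SAP then summarizes adverse events by treatment group and overall in the Safety Population.

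**The concern.** A treatment-emergent rule should count an event under the treatment that brought it on or made it worse. The lead-in does this, but the attached condition admits only events whose onset falls on or after treatment start. An event that was already present and then worsened has an earlier onset, so it fails.

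This matters more here than in a parallel-group trial. Each patient has five dosing periods with different treatments, so there are four boundaries at which a continuing event could worsen under a new treatment. Protocol 2.2 hypothesizes that the safety and tolerability of a combination are no worse than the cumulative findings on the two monotherapies. By-treatment event counts are evidence on that question, so the rule that assigns an event to a treatment should work as intended. The SAP's intensity table also classifies patients by their most intense occurrence. If a single record holds the maximum grade, a worsening in a later period could appear under the earlier treatment.

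**Working it through.** The plan gives no figure to reproduce. The check is a logical one, followed by worked cases.

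**Logic.** For a period starting on day s with its window ending on day e, let o be the onset day and w the day of worsening.

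- Lead-in: o ≥ s, or w ≥ s.
- Date condition: s ≤ o ≤ e.
- SAP rule: lead-in and date condition together.

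Whenever the date condition is true, o ≥ s is true, so the lead-in is already met and w plays no part. The SAP rule reduces to s ≤ o ≤ e, which is the on-therapy rule. The protocol definition, applied per period, is s ≤ o ≤ e or s ≤ w ≤ e.

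**Inputs for the worked cases.** Screening on days -18 to -1, five two-day periods and washouts of 7 to 21 days come from Protocol section 3. Three things are assumed: every washout is 14 days (the midpoint), treatment start is taken per period, and the last window runs to 30 days after the last dose.

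- Period starts: 1 + 16 × (i − 1), giving days 1, 17, 33, 49 and 65.
- Window ends for periods 1 to 4: start + 15, giving days 16, 32, 48 and 64.
- Window end for period 5: last dose on day 66, and 66 + 30 = day 96.

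| Case | Onset day | Worsening day | SAP as written: period credited | Protocol definition: period credited |
|---|---|---|---|---|
| New in period 1 | 1 | none | 1 | 1 |
| Starts and worsens in period 1 | 1 | 2 | 1 | 1 |
| Starts in screening, worsens in period 1 | -5 | 1 | none | 1 |
| Starts in screening, worsens in period 3 | -5 | 33 | none | 3 |
| Starts in period 1, worsens in period 2 | 2 | 17 | 1 | 1 and 2 |
| Starts in period 4, worsens in period 5 | 50 | 65 | 4 | 4 and 5 |

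Over every pair of onset and worsening days from day -18 to day 96, the increase-in-intensity wording changed the SAP classification in 0 pairs, as the logic requires.

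**If treatment start means the first study dose.** The SAP does not define the term per period. On this reading, screening-onset events that worsen on drug still fail. A worsening in a later period still has no rule assigning it to the treatment then being given.

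**The case against.** The strongest reply is that this is a drafting slip whose effect depends on how events are recorded. The lead-in matches the protocol, so a reader might infer that the sponsor chose to drop worsening. The documents do not support that: the conflict lies between the lead-in and its own condition, and SAP 5.2.2 lists no such change. SAP 6.4 gives rules for event start and end dates and mentions no date of worsening. With that structure the lead-in can work only if each worsening is entered as a new record with its own start date, and the rule would then be correct. The eCRF instructions are not among the documents, the output specifications are in a separate document, and parts of the SAP's safety text are withheld. All of this stands, but no readable text in Protocol 9.1.1, Protocol 9.2 or SAP section 6 states that convention. If it exists, the SAP should say so.

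The class lost altogether is also narrow. Conditions present before the Screening Visit are medical history. Only events that start between consent or screening and first dose, a span of about 18 days, and then worsen are never counted. An event that starts in one period and worsens in a later one remains treatment-emergent; only its attribution suffers.

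A reader might further infer that the 30-day limit lets one event count under several later treatments. The wording reads more naturally as two cases: the washout limit where another period follows, and 30 days after the patient's final dose. That reading gives no overlap, so the upper limit needs at most a clarifying phrase.

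**Conclusion.** The point holds. Taken literally, the date condition in Table 5-23 makes the worsening clause inoperative, contrary to the table's lead-in and to the Protocol Summary. Screening-onset events that worsen on drug are never treatment-emergent. Events that worsen in a later period are credited only to the earlier treatment.

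This rests on two assumptions: that treatment start is meant per dosing period, as the washout limit implies, and that a worsening is not re-entered as a new record.

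The size cannot be computed, because the documents give no rate of pre-existing or worsening events. It may be small: dosing lasts two days, washouts are 7 to 21 days, and an event would have to persist to the next dose and then worsen. Event durations are not given either. A reader might infer a material distortion of the safety comparison, but the documents do not support that, and the adverse event summaries are descriptive with no test attached. It is still more than missing detail, because a stated rule would misclassify events whenever they occur.

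**What to change.** In the treatment-emergent row of Table 5-23, apply the per-period window to the event start date or the date of increase in intensity, and credit a worsening to the period in which it occurs. If the eCRF holds no date of worsening, state instead that each worsening is entered as a new adverse event record whose start date is the date of worsening. Keep the on-therapy row as start-date only. As clarifications, state that treatment start date is per dosing period and that the 30-day limit applies after the patient's last study dose.

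The cost is one table edit and a change to the flag programming, provided the worsening is dated in the data. No readable passage shows that such a date is collected; if it is not, a recording convention is also needed. The downside is that one event may appear under two treatments, once as new and once as worsened, and a table footnote should say so.
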